##### a. Background

Various diabetic footwear has been created to help prevent foot ulceration by reducing peak pressures, which are typically passive. Many patients who are prescribed pressure-reducing insoles/footwear still develop foot ulcers most likely due to the complicated pathology of ulcers. Diabetic foot ulcers have a multifactorial etiology that involves elevated pressure, shear, and/or prolonged or repetitive mechanical loading on the same area of the plantar surface. This is particularly apparent in patients suffering from peripheral neuropathy who fail to adjust their stance or gait to relieve stress upon sensitive areas because of their lack of sensation.

In order to effectively prevent foot ulceration, one needs to address as many causative factors as possible in a therapeutic device. We propose a preventive footwear that will address at least four causative factors; (i) elevated peak pressures, (ii) elevated shear stresses, (iii) repetitive loading of certain plantar regions and (iv) prolonged ischemia at certain locations of the foot. The first two factors will be addressed by maximizing the plantar surface area. By increasing available surface area that bears forces, we will reduce stress magnitudes. We will also incorporate a gel material that will help achieve this goal, as well as act as a shock absorber.

The primary novelty of our proposed design will be addressing repetitive application of mechanical stresses on the plantar surface. We believe it would be beneficial to develop an automated insole system capable of cyclically shifting the mechanical loading experienced by the foot to different areas of the plantar surface at a prescribed frequency while walking/standing. Additionally, this insole could provide continuous load relief to sensitive areas as needed; for instance, inside a Total Contact Cast (TCC) where ulcers already exist. Ulcer areas can be gradually loaded in a TCC using the insole, making tissue adapt to mechanical stresses.

If future research demonstrates that ulcers develop at peak shear stress sites and/or locations that experience abnormal temperatures, PAS shoes can be used to off-load such locations to prevent a predicted ulcer. PAS may also be used in the future to minimize incidence of metatarsal stress fractures.

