### 3. Study Design.

Describe the study design (e.g., single/double blind, parallel, crossover, etc.) Consider inserting a scheme to visually present the study design.

The overall purpose of this clinical trial is to develop and test Pressure Alternating Shoes (PAS), which will periodically off-load certain regions of the foot in order to prevent foot ulcers. We will utilize an automated dual layer insole comprised of an active pressurized actuator array in combination with a passive compliant layer on top of each actuator to modulate and distribute the plantar surface pressure as desired. This device will allow us to simultaneously load and offload select areas of the foot using the active layer by inflating and deflating individual actuators using pressurized air. After offloading, the remaining load will be distributed to other areas with inflated actuators. Automatic modulation will be provided through programmable control hardware which will cyclically relieve mechanical loading based on a prescribed duration and frequency.

We will report the mechanical and physical characteristics of our dual layer insole structure and evaluate its safety, usability, and comfort with healthy and diabetic subjects. To our knowledge, this will be the first study on the effect of a device actively modulating mechanical loading at the plantar surface for foot ulcer prevention. This system will allow for a systematic study of cyclical offloading in ulcer prevention.

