### 4. Research Plan / Description of the Research Methods:

#### 4.a. Provide a comprehensive narrative describing the research methods.

- 1) Provide the order in which tests/procedures will be performed,
- 2) Provide the setting for these events and a description of the methods used to protect privacy during the study.
- 3) Provide the plan for data analysis (include as applicable the sample size calculation)

Please respond to all components of this item, or clearly indicate which components are not applicable.

A two-tier human subjects study will be conducted to assess the biomechanical characteristics of PAS. All subjects will be assigned a study number. Data will be collected on paper forms and kept in subject binders in a locked research office. Forms will be scanned to a password-protected drive. In the first tier we will test PAS in healthy subjects. Exclusion criteria will be diabetes and foot complications. On the right foot, subject will wear diabetic footwear equipped with PAS device, and on the left foot, subjects will wear diabetic footwear equipped with PAS sealed at ambient pressure. Pressure sensing insoles (Pedar, NovelUSA, MN) will be placed between the foot and the insole and subjects will be asked to walk on a treadmill at self-selected speeds for 5 minutes. During minutes 0:30-4:30, each of the active cells of PAS will be offloaded consecutively for 30 seconds. Five mid-gait steps from each offloading period will be evaluated for each subject. Pressure values in the selected 5 steps will be averaged and a mean pressure profile will be obtained. Subjects will then be asked to walk with their daily shoes on the treadmill for 5 minutes at self-selected speeds. This additional session will provide control data for comparison. The order of the sessions will be randomized.

We will assess insole plantar pressures using a Tekscan pressure mapping (Tekscan, Inc., Norwood, MA) and XSENSOR (XSENSOR Technology Corporation, Calgary, Canada). Body-worn sensors (BalanSens, BioSensics, Watertown, MA, USA) will be used to measure static (postural sway) conditions. Postural sway and estimated Center of Mass (COM) will be quantified with the body-worn sensors with (i) eyes-open, firm surface in normal gait pattern on a straight path...

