**Data Analysis:** All subjects will be assigned a study number. Data will be collected on paper forms and kept in subject binders in a locked research office. Forms will be scanned to a password-protected drive. For analysis purposes, de-identified data will be shared with the University of Texas Health Science Center at San Antonio. As all data will be de-identified, subjects will not need to be reconstituted. A study by Bus et al [32] compared a group of subjects in custom-made footwear versus standard therapeutic footwear. Results indicated  $221 \pm 51$  kPa pressure in custom shoes vs  $274 \pm 66$  kPa in standard shoes ( $p < .001$ ) in a total of 171 subjects. To detect a similar difference, at 85% power and type I error rate of 1.7%, a sample size of 18 is sufficient for a within subjects analysis (paired t-tests). Alpha was adjusted using a Bonferroni correction since there are three primary variables of interest; peak pressure, RMSE and velocity of COP. Due to limitations in tissue perfusion measurement which cannot be acquired in real time (inside the shoe), the Oxy variable will not be a primary variable of interest. For balance variables, our study will have a power of 80% to detect an effect size of 0.8 if we increase the sample size to 20. Two previous studies revealed a comparable effect size when authors compared balance between the use of various diabetic insoles and control insoles [33,34]. Therefore we will recruit 20 healthy subjects in the first tier and 10 diabetic neuropathic subjects in the second tier (total N=30). Investigation of diabetic neuropathic subjects will further increase the statistical power and hence we will not account for a potential drop-out which may reduce the sample size by approximately 10%. Moreover, for pilot/proof of concept studies, it has been suggested in the literature that a minimum of 10% of subjects of the larger parent clinical trial should be studied [35]. A future clinical trial with PAS will be very similar to the study by Bus et al [32]. Hence even after a 10% dropout, we will still meet this 10% rule for a pilot study. In case the data does not follow normal distribution, we will use the non-parametric Signed Rank test to compare the differences. Our expectation is that we will observe only non-significant differences in comparing pressure and balance between PAS and control shoes as we do not expect PAS to impair gait of subjects.

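### The plan has only difference tests and expects them to be non-significant because PAS should not impair gait; without confidence intervals, non-significance alone would not support no impairment

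*Combined protocol and SAP*

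**What the plan says.** Everything on analysis is in the Data Analysis paragraph of section 4.a.

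- **Tests.** Three primary variables (peak pressure, RMSE, velocity of COP) are compared within subject by paired t-test, with a Bonferroni-adjusted level of 1.7%. If normality fails, "we will use the non-parametric Signed Rank test to compare the differences".
- **Sizing for peak pressure.** The planning values are 221 ± 51 and 274 ± 66 kPa, a difference of 53 kPa. "To detect a similar difference, at 85% power and type I error rate of 1.7%, a sample size of 18 is sufficient".
- **Sizing for balance.** "our study will have a power of 80% to detect an effect size of 0.8 if we increase the sample size to 20".
- **Subjects.** 20 healthy (tier 1) and 10 diabetic neuropathic (tier 2). The second group is said to add power, and a dropout of about 10% is not added to the sample size.
- **Reading of the result.** The closing sentence expects "only non-significant differences in comparing pressure and balance between PAS and control shoes as we do not expect PAS to impair gait of subjects".

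Section 3 gives as one purpose to "evaluate its safety, usability, and comfort with healthy and diabetic subjects". The available text has no confidence interval, no plan to estimate an effect, and no equivalence or non-inferiority margin. Some pages were not available, so this absence is judged on what can be read.

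**The concern.** Both planned tests ask whether the data contradict a zero difference. Failing to contradict zero differs from showing that any difference is small, and in small samples the two can be far apart. The closing sentence ties non-significance to an absence of gait impairment, and nothing else in the plan says how a null result should be read. If the expected result occurs, the plan yields a p-value above 1.7% and nothing that shows which degrees of worsening the data rule out.

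This matters because safety is a stated purpose, the diabetic neuropathic group is small, and the plan presents the study as a pilot for a larger trial. That later trial needs estimates and their precision more than a list of non-significant tests.

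**Working it through.** **Inputs from section 4.a:** test level 0.017; n = 20 and n = 10 by tier, 30 in total; 18 is both the pressure sample size and 20 less 10% dropout; balance effect size 0.8; pressure 221 (SD 51) and 274 (SD 66) kPa.

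**Assumptions:** two-sided tests (sidedness is not stated); effects in SDs of the paired difference; a within-subject correlation r, which is not stated and is shown as a range. A 0.5 SD shift is illustrative and not from the documents.

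**Step 1. Reproduce the plan's figures.** Paired t-test power comes from the noncentral t distribution with n − 1 degrees of freedom and noncentrality d√n.

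- Balance: d = 0.8, n = 20 gives 82.1% (n = 19 gives 79.4%). This agrees with the stated 80% at 20.
- Pressure: SD of the difference = √(51² + 66² − 2r·51·66). At r = 0.5 this is √3591 = 59.9 kPa, so d = 53/59.9 = 0.884, and n = 18 gives 85.2%. This agrees with the stated 85% at 18. Solved backwards, 85% at n = 18 needs d = 0.882, so SD = 53/0.882 = 60.1 kPa and r is about 0.50.

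The stated sample sizes therefore hold as sizes for difference tests.

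**Step 2. How often a real shift is non-significant.** P = F(t_crit) − F(−t_crit), with F the noncentral t distribution function.

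| n | t_crit | true 0.8 SD | true 0.5 SD |
|---|---|---|---|
| 20 (tier 1) | 2.616 | 18% | 62% |
| 18 (tier 1 after 10% dropout) | 2.645 | 24% | 67% |
| 10 (tier 2 tested alone) | 2.921 | 60% | 85% |
| 30 (tiers pooled) | 2.532 | 4% | 41% |

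**Step 3. What the interval would show.** The half-width of the 98.3% interval is t_crit/√n, in SDs of the paired difference.

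- n = 20: 2.616/√20 = 0.585.
- n = 10: 2.921/√10 = 0.924.

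In kPa, multiply by the SD of the difference:

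| r | SD of difference | n = 20 | n = 10 |
|---|---|---|---|
| 0.3 | 70.3 | 41 | 65 |
| 0.5 | 59.9 | 35 | 55 |
| 0.6 | 54.0 | 32 | 50 |
| 0.7 | 47.4 | 28 | 44 |

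**Step 4. Which non-significant results exclude the planning effects.**

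- *n = 20.* An observed difference near zero excludes 0.8 SD (0.585 < 0.8) and 53 kPa (28 to 41 < 53). The upper limit reaches 0.8 SD once the observed shift toward harm is 0.8 − 0.585 = 0.215, about 0.22 SD. It reaches 53 kPa at 53 − 35 = 18 kPa when r = 0.5. Results from there up to 0.585 SD (35 kPa) are non-significant and do not exclude the planning effect.
- *n = 10.* Because 0.924 > 0.8, even an observed zero does not exclude 0.8 SD. Whether an observed zero excludes 53 kPa depends on r: not at 0.3 or 0.5, but yes at 0.6 or 0.7.

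**Step 5. How often n = 20 is informative.** If there is truly no difference, the 98.3% upper limit falls below 0.8 SD 82% of the time. It falls below 53 kPa about 89% of the time at r = 0.5.

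**The case against.** The best defence is that the plan never draws the faulty inference. It reasons forward: no impairment is expected, so no significant difference is expected. A reader might infer that the investigators will declare PAS harmless on a null p-value. The documents do not say so, and no stated safety or efficacy decision rests on the test. That stands. What remains is that the sentence is the only guide to interpretation and invites the faulty reading.

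Three stronger readings are tempting and not supported.

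- *Any null result is compatible with the effects the study was sized to detect.* This is false for the healthy tier. With 20 subjects, an observed difference near zero excludes both 0.8 SD and 53 kPa. The problem is confined to results that lean toward harm, and to n = 10.
- *The diabetic tier will miss a 0.8 SD worsening 60% of the time.* This holds only if that tier is tested alone. The remark that diabetic subjects add power points toward pooling, where the figure is 4% for 0.8 SD, though still 41% for 0.5 SD. Whether pooling is sound is a separate question.
- *Sizing on a 53 kPa difference contradicts expecting none, particularly as the Background says "By increasing available surface area that bears forces, we will reduce stress magnitudes".* That line is device rationale and not an analysis hypothesis. A two-sided test needs no stated direction, and sizing a study to detect a change one hopes not to see can be sound.

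It is also fair that this is a pilot described on an IRB form. That argues for a small change in wording, not for an equivalence trial.

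**Conclusion.** The point holds in a limited form. The plan relies on difference tests alone, and its one remark on interpretation links non-significance to no impairment. Used that way, a null p-value would be an unsound basis: adequate against a large shift in the pooled sample, weaker in 20 subjects, and poor in 10. An interval separates the informative null results from the uninformative ones, and the p-value does not.

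The miss rates and SD-unit half-widths rest on two-sided testing at 1.7%. The kPa figures also rest on the unstated correlation; the pressure conclusion for an observed zero holds at n = 20 across 0.3 to 0.7 but changes within that range at n = 10. No error in the stated sample sizes is implied, and the documents supply no margin against which no impairment could be formally claimed. This is a cheap improvement.

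**What to change.** Replace the last sentence of the Data Analysis paragraph in section 4.a with:

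> For each primary variable we will report the paired difference (PAS minus control) with a two-sided 98.3% confidence interval, matching the 1.7% test level (Hodges-Lehmann interval if the Signed Rank test is used), overall for any pooled analysis and separately by tier. Non-significance will not be read as absence of impairment; results will be interpreted from the interval, and the diabetic tier is estimation only.

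The 98.3% level keeps interval and test in agreement. At n = 20 it is 25% wider than a 95% interval (0.585/0.468 = 1.25).

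**Cost.** Wording only, with no extra subjects or measurements. The intervals will be wide: half-width 0.58 SD at n = 20 (0.62 with 18 completers) and 0.92 SD at n = 10 (1.00 with 9 completers). A null p-value can no longer be offered as evidence of no impairment.

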**Form A**

**IRB # STU-2022-1038 Pressure Alternating Shoes (PAS) for Prevention of Diabetic Foot Ulcers**

**4.b. List of the study intervention(s) being tested or evaluated under this protocol**

 N/A - this study does not test or evaluate an intervention. Skip to item 4.d.			
#	Study intervention(s) being tested or evaluated under the protocol  Add or delete rows as needed	Affiliate	Local Standard Practice? Indicate whether the intervention is considered acceptable practice locally for applicable institutions
1	Treadmill walk for 5 minutes at self-determined speed with Control footwear which is comprised of extra-extra depth diabetic shoes for men and women and commonly used multilayer off-the-shelf diabetic orthotics. The shoes will be the same make and model that will accommodate the PAS. Pressure sensing insoles (Pedar, NovelUSA, MN) will be placed between the foot and the insole	 UTSW  PHHS  CMC  THR  TSRH  Other: SHP	 Yes  Yes  Yes  Yes  Yes  Yes
2	Treadmill walk for 5 minutes at self-determined speed with their daily shoes	 UTSW  PHHS  CMC  THR  TSRH  Other: SHP	 Yes  Yes  Yes  Yes  Yes  Yes
3	Pressure mapping using a TekScan (TekScan, Inc., Norwood, MA) and body worn sensors (BalanSens, BioSensics, Watertown, MA, USA) in kinetic (postural sway) condition. This will be done twice, once in PAS and once using daily shoes.	 UTSW  PHHS  CMC  THR  TSRH  Other: SHP	 Yes  Yes  Yes  Yes  Yes  Yes
4	Baseline oxyhemoglobin (Oxy) values of both feet will be captured with a portable hyperspectral camera and again after 5 minute treadmill walk (SnapShot NIR, Kent Imaging, Calgary, Canada).	 UTSW  PHHS  CMC  THR  TSRH  Other: SHP	 Yes  Yes  Yes  Yes  Yes  Yes
5	Temperature of the sole of the feet will be measured using a commercial infrared thermal camera after treadmill walk (FLIR Systems, OR).	 UTSW  PHHS  CMC  THR  TSRH  Other: SHP	 Yes  Yes  Yes  Yes  Yes  Yes

**Form A**

**IRB #** **STU-2022-1038 Pressure Alternating Shoes (PAS) for Prevention of Diabetic Foot Ulcers**

6	Magnetic resonance imaging will be performed of the foot and ankle	 UTSW	 Yes
		 PHHS	 Yes
		 CMC	 Yes
		 THR	 Yes
		 TSRH	 Yes
		 Other: SHP	 Yes

**4.c. Risk:Benefit Analysis of study interventions being tested or evaluated under this protocol**

For each study intervention identified in section 6b above, complete a risk:benefit analysis table.

*(Two tables are provided, copy & paste additional tables as needed or delete both tables if this study does not test an intervention)*

**4.c.**

**Study Intervention #1**

Treadmill walk in PAS

List each group exposed to this intervention on a separate line. (e.g., experimental, control, Arm A, Arm B, etc) Or state All Groups/Subjects	For each group, list the benefits of this intervention. (Benefits can be directly from the intervention or from a monitoring procedure likely to contribute to the subject's well being). If there are no benefits, state "none".
All Subjects	None

**If you are requesting a Waiver of Informed Consent, complete the table below.**

If you have a consent form, list the reasonably foreseeable **risks** in the consent form (and do not complete this section).

List the risks according to the probability (likely, less likely or rare) and magnitude (serious or not serious).  
(include: 1) expected adverse events; 2) rare and serious adverse events; 3) all other psychological, social, legal harms)  
Do not delete frequency. Frequency must be estimated because it will assist you with determining which adverse events will require prompt reporting.

	Not serious	Serious
Likely These risks are expected to occur in more than 20 out of 100 subjects.	•	•
Less likely These risks are expected to occur in 5-20 subjects or less out of 100 subjects.	•	•
Rare These risks are expected to occur in less than 5 subjects out of 100		•

**Form A**

IRB #	STU-2022-1038 Pressure Alternating Shoes (PAS) for Prevention of Diabetic Foot Ulcers
-------	---------------------------------------------------------------------------------------

**4.c.**

**Study Intervention #2**

Treadmill walk in daily shoes

List each group exposed to this intervention on a separate line. (e.g., experimental, control, Arm A, Arm B, etc) Or state All Groups/Subjects	For each group, list the benefits of this intervention. (Benefits can be directly from the intervention or from a monitoring procedure likely to contribute to the subject's well being). If there are no benefits, state "none".
All Groups	None

**If you are requesting a Waiver of Informed Consent, complete the table below.**

If you have a consent form, list the reasonably foreseeable **risks** in the consent form (and do not complete this section).

List the risks according to the probability (likely, less likely or rare) and magnitude (serious or not serious).

(include: 1) expected adverse events; 2) rare and serious adverse events; 3) all other psychological, social, legal harms)

Do not delete frequency. Frequency must be estimated because it will assist you with determining which adverse events will require prompt reporting.

	Not serious	Serious
Likely These risks are expected to occur in more than 20 out of 100 subjects.	•	•
Less likely These risks are expected to occur in 5-20 subjects or less out of 100 subjects.	•	•
Rare These risks are expected to occur in less than 5 subjects out of 100		•

**Form A**

IRB #	STU-2022-1038 Pressure Alternating Shoes (PAS) for Prevention of Diabetic Foot Ulcers
-------	---------------------------------------------------------------------------------------

**4.c.**

**Study Intervention #3**

Pressure mapping and Balance testing

List each group exposed to this intervention on a separate line. (e.g., experimental, control, Arm A, Arm B, etc) Or state All Groups/Subjects	For each group, list the benefits of this intervention. (Benefits can be directly from the intervention or from a monitoring procedure likely to contribute to the subject's well being). If there are no benefits, state "none".
All Groups	None

**If you are requesting a Waiver of Informed Consent, complete the table below.**

If you have a consent form, list the reasonably foreseeable **risks** in the consent form (and do not complete this section).

List the risks according to the probability (likely, less likely or rare) and magnitude (serious or not serious).

(include: 1) expected adverse events; 2) rare and serious adverse events; 3) all other psychological, social, legal harms)

Do not delete frequency. Frequency must be estimated because it will assist you with determining which adverse events will require prompt reporting.

	Not serious	Serious
Likely These risks are expected to occur in more than 20 out of 100 subjects.	•	•
Less likely These risks are expected to occur in 5-20 subjects or less out of 100 subjects.	•	•
Rare These risks are expected to occur in less than 5 subjects out of 100		•

